7.2 Serious adverse events

7.2.1 Definition of SAE

An SAE is defined as any adverse event [appearance of (or worsening of any pre-existing)] undesirable sign(s), symptom(s) or medical conditions(s)) which meets any one of the following criteria:

- is fatal or life-threatening
- results in persistent or significant disability/incapacity
- constitutes a congenital anomaly/birth defect

- requires inpatient hospitalization or prolongation of existing hospitalization, unless hospitalization is for:
 - routine treatment or monitoring of the studied indication, not associated with any deterioration in condition (specify what this includes)
 - elective or pre-planned treatment for a pre-existing condition that is unrelated to the indication under study and has not worsened since signing the informed consent
 - treatment on an emergency outpatient basis for an event not fulfilling any of the definitions of a SAE given above and not resulting in hospital admission
 - social reasons and respite care in the absence of any deterioration in the patient's general condition
- is medically significant, e.g. defined as an event that jeopardizes the patient or may require medical or surgical intervention.

All malignant neoplasms will be assessed as serious under "medically significant" if other seriousness criteria are not met.

Life-threatening in the context of a SAE refers to a reaction in which the patient was at risk of death at the time of the reaction; it does not refer to a reaction that hypothetically might have caused death if it were more severe (see Annex IV, International Conference on Harmonization of Technical Requirements for Registration of Pharmaceuticals for Human Use (ICH)-E2D Guideline).

Medical and scientific judgment should be exercised in deciding whether other situations should be considered serious reactions, such as important medical events that might not be immediately life threatening or result in death or hospitalization but might jeopardize the patient or might require intervention to prevent one of the other outcomes listed above. Examples of such events are intensive treatment in an emergency room or at home for allergic bronchospasm, blood dyscrasias or convulsions that do not result in hospitalization or development of dependency or abuse (see Annex IV, ICH-E2D Guideline).

Any suspected transmission via a medicinal product of an infectious agent is also considered a serious adverse reaction.

7.2.2 SAE reporting

To ensure patient safety, every SAE, regardless of causality, occurring after the patient has provided informed consent and until 12 weeks after last administered dose of study treatment or 30 days after the subject has stopped study participation (whichever is later) must be reported to Novartis within 24 hours of learning of its occurrence. Any SAEs experienced after this period should only be reported to Novartis if the Investigator suspects a causal relationship to study treatment.

All follow-up information for the SAE including information on complications, progression of the initial SAE and recurrent episodes must be reported as follow-up to the original episode within 24 hours of the Investigator receiving the follow-up information. An SAE occurring at a different time interval or otherwise considered completely unrelated to a previously reported one must be reported separately as a new event.

Information about all SAEs is collected and recorded on the Serious Adverse Event Report Form; all applicable sections of the form must be completed in order to provide a clinically thorough report. The Investigator must assess the relationship of each SAE to the study treatment, complete the SAE Report Form in English, and submit the completed form within 24 hours to Novartis. Detailed instructions regarding the submission process and requirements for signature are to be found in the Investigator folder provided to each site.

Follow-up information is submitted as instructed in the Investigator folder. Each re-occurrence, complication, or progression of the original event must be reported as a follow-up to that event regardless of when it occurs. The follow-up information should describe whether the event has resolved or continues, if and how it was treated, whether the blind was broken or not, and whether the patient continued or withdrew from study participation.

If the SAE is not previously documented in the Investigator's Brochure or Package Insert (new occurrence) and is thought to be related to the study treatment a Drug Safety and Epidemiology Department associate may urgently require further information from the Investigator for health authority reporting. Novartis may need to issue an Investigator Notification (IN) to inform all investigators involved in any study with the same study treatment that this SAE has been reported. Suspected Unexpected Serious Adverse Reactions (SUSARs) will be collected and reported to the competent authorities and relevant ethics committees in accordance with EU Guidance 2011/C 172/01 or as per national regulatory requirements in participating countries.

7.3 Liver safety monitoring

To ensure patient safety and enhance reliability in determining the hepatotoxic potential of an investigational drug, a standardized process for identification, monitoring and evaluation of liver events has to be followed.

The following two categories of abnormalities / adverse events have to be considered during the course of the study (irrespective of whether classified/reported as (S)AE):

- Liver laboratory triggers, which will require repeated assessments of the abnormal laboratory parameter
- Liver events, which will require close observation, follow-up monitoring and completion of the standard base liver CRF pages

Please refer to [Table 14-1](#) in [Appendix 2](#) for complete definitions of liver laboratory triggers and liver events.

Every liver laboratory trigger or liver event as defined in [Table 14-1](#) of [Appendix 2](#) should be followed up by the Investigator or designated personal at the trial site as summarized below. Detailed information is outlined in [Table 14-1](#) in [Appendix 2](#).

For the liver laboratory trigger:

- Repeating the liver function test (LFT) within the next week to confirm elevation.

These LFT repeats must be performed using the central laboratory if possible. If this is not possible, then the repeats can be performed at a local laboratory to monitor the safety of the patient. Repeats laboratory must then be performed at central laboratory as soon as possible. If

a liver event is subsequently reported, any local LFTs previously conducted that are associated with this event must be reported on the Liver CRF pages.

- If the elevation is confirmed, close observation of the patient will be initiated, including consideration of treatment interruption if deemed appropriate.

For the liver events:

- Repeating the LFT to confirm elevation as appropriate
- Discontinuation of the investigational drug if appropriate
- Hospitalization of the patient if appropriate
- A causality assessment of the liver event via exclusion of alternative causes (e.g., disease, co-medications)
- An investigation of the liver event which needs to be followed until resolution.

These investigations can include serology tests, imaging and pathology assessments, hepatologist's consultancy, based on investigator's discretion. All follow-up information, and the procedures performed must be recorded on appropriate CRF pages, including the liver event overview CRF pages.

7.4 Renal safety monitoring

The following two categories of abnormal renal laboratory values have to be considered during the course of the study:

- Serum event:
 - confirmed (after $\geq 24\text{h}$) increase in serum creatinine of $\geq 25\%$ compared to baseline which exceeds the normal limits for the patient's gender and age during normal hydration status and continues for ≥ 3 consecutive months.
- Urine event
 - new onset ($\geq 1+$) proteinuria; confirmed by doubling in the urinary albumin-creatinine ratio (ACR) or urinary protein-creatinine ratio (PCR) (if applicable)
 - new onset ($\geq 1+$), hematuria or glycosuria

Every renal laboratory trigger or renal event as defined in [Table 15-1](#) in [Appendix 3](#) should be followed up by the Investigator or designated personnel at the trial site as summarized in [Appendix 3](#).

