The following defined notable laboratory or vital sign abnormalities, except creatinine clearance, will be communicated at the same time as they are sent to investigators to Novartis. Novartis will determine if further consultations with Investigator(s) are appropriate.

Laboratory Criteria

Newly occurring selected notable laboratory abnormalities in pediatric patients at the time of the assessment:

Biochemistry

- Alanine aminotransferase (ALT)(SGPT):
 - > Upper Limit of Normal (ULN)
 - $\geq 3 \times$ ULN
 - $\geq 5 \times$ ULN
 - $\geq 8 \times$ ULN
 - $\geq 10 \times$ ULN
- Aspartate aminotransferase (AST) (SGOT):
 - >ULN
 - $\geq 3 \times$ ULN
 - $\geq 5 \times$ ULN
 - $\geq 8 \times$ ULN
 - $\geq 10 \times$ ULN
- Total Bilirubin (TBL)
 - >ULN,
 - $\geq 1.5 \times$ ULN,
 - $\geq 2 \times$ ULN
- ALP
 - >ULN
 - $\geq 1.5 \times$ ULN,
 - $\geq 2 \times$ ULN,
 - $\geq 3 \times$ ULN
 - $\geq 5 \times$ ULN
- ALT and/or AST $>3 \times$ -, $5 \times$ -, $10 \times$ ULN accompanied by TBL $>2 \times$ ULN
- ALT or AST $>3 \times$ ULN and TBL $>2 \times$ -, and ALP $>2 \times$ ULN.
- ALP $>3 \times$ ULN and TBL $>2 \times$ ULN

- Gamma-Glutamyltransferase (GGT):
 - >ULN
 - $\geq 3 \times \text{ULN}$
 - $\geq 5 \times \text{ULN}$
- Creatinine (serum): $\geq 1.5 \times \text{ULN}$
- Creatinine clearance (Schwartz formula[§]): $\geq 25\%$ decrease from baseline, ≥ 3 months in duration
- Protein urine dipstick:
New protein $\geq 1+$, ≥ 3 months in duration
- Creatinine clearance (Schwartz formula[§]): $\geq 25\%$ decrease from baseline, ≥ 3 months in duration in combination with protein urine dipstick resulting in new protein $\geq 1+$, ≥ 3 months in duration
- Total Cholesterol: $\geq 1.5 \times \text{ULN}$
- Triglycerides: $\geq 5.7 \text{ mmol/L}$.

[§]Schwartz formula- Creatinine clearance (mL/min/1.73m²) was derived using the following formula $0.413 \times \text{length (cm)} / (\text{serum creatinine (mg/dL})$ ([Schwartz et al 2009](#)).

For creatinine clearance only, baseline value for the decrease from baseline criterion will be calculated as the average of all values prior to the first dose (i.e. screening and baseline values).

Hematology

- Hemoglobin: $\geq 20 \text{ g/L}$ decrease from baseline,
or $< 85 \text{ g/L}$ for < 16 years of age
 $< 100 \text{ g/L}$ for ≥ 16 years of age
- Absolute neutrophils:
 - Grade 1: $< \text{LLN} - 1.5 \times 10\text{E}9/\text{L}$
 - Grade 2: $< 1.5 - 1.0 \times 10\text{E}9/\text{L}$

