^aElevated ALT/AST > 3 × ULN and TBL > 2 × ULN but without notable increase in ALP to > 2 × ULN

^b(General) malaise, fatigue, abdominal pain, nausea, or vomiting, or rash with eosinophilia

^cResolution is defined as an outcome of one of the following: (1) return to baseline values, (2) stable values at three subsequent monitoring visits at least 2 weeks apart, (3) remain at elevated level after a maximum of 6 months, (4) liver transplantation, and (5) death.

15 Appendix 3: Specific Renal Alert Criteria and Actions

Table 15-1 Specific Renal Alert Criteria and Actions

Serum Event	
Serum creatinine increase 25 – 49% compared to baseline and is above ULN	Confirm 25% increase after 24-48h Follow up within 2-5 days
Acute Kidney Injury: Serum creatinine increase ≥ 50% compared to baseline and is above the ULN	Follow up within 24-48h if possible Consider study treatment interruption Consider patient hospitalization /specialized treatment
Urine Event	
New dipstick proteinuria ≥1+ Albumin- or Protein-creatinine ratio increase ≥ 2-fold Albumin-creatinine ratio (ACR) ≥ 30 mg/g or ≥ 3 mg/mmol; Protein-creatinine ratio (PCR) ≥ 150 mg/g or > 15 mg/mmol	Confirm value after 24-48h Perform urine microscopy Consider study treatment interruption / or discontinuation
New dipstick glycosuria ≥ 1+ not due to diabetes	Blood glucose (fasting) Perform serum creatinine, ACR
New dipstick hematuria ≥ 1+ not due to trauma	Urine sediment microscopy Perform serum creatinine, ACR
For all renal events:	

Document contributing factors in the CRF: co-medication, other co-morbid conditions, and additional diagnostic procedures performed
 
Monitor patient regularly (frequency at investigator's discretion) until either:
 
Event resolution: sCr within 10% of baseline or protein-creatinine ratio within 50% of baseline, or
 
Event stabilization: sCr level with ±10% variability over last 6 months or protein-creatinine ratio stabilization at a new level with ± 50% variability over last 6 months.
	

16 Appendix 4: Weight ranges: recommended maximum sample blood volume per blood draw

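### Section 7.4 requires a renal serum event to last at least 3 months, while Table 15-1, which it names as the source of the definition, sets no duration and asks for action within days

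*Protocol*

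**What the plan says.** Section 7.4 lists two categories of abnormal renal laboratory values, serum and urine. The serum event is a creatinine increase of at least 25% over baseline, confirmed after at least 24 hours, "which exceeds the normal limits for the patient's gender and age during normal hydration status and continues for" at least 3 consecutive months. The section closes with its only instruction on action: "Every renal laboratory trigger or renal event as defined in" Table 15-1 is to be followed up as Appendix 3 sets out.

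Table 15-1 has its own serum event heading with two tiers:

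- A rise of 25-49% "compared to baseline and is above ULN". Action: "Confirm 25% increase after 24-48h Follow up within 2-5 days".
- "Acute Kidney Injury: Serum creatinine increase" of at least 50% "compared to baseline and is above the ULN". Action: "Follow up within 24-48h if possible", with interruption of study treatment and hospitalization to be considered.

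Neither tier has a duration. For all renal events the table also requires contributing factors to be documented in the CRF, and regular monitoring until the event resolves or stabilises.

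**The concern.** One label carries two definitions, and the section that gives the first also names the second as the source. They select different children: the Section 7.4 text keeps only sustained rises, while Table 15-1 includes any rise of sufficient size above the upper limit of normal.

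The CRF documentation and monitoring duties in Table 15-1 apply to renal events, so the definition a site uses decides which creatinine rises receive them. Section 7.4 is a section that sites will consult: Section 6.5.5.3 directs them to it when a urine dipstick is positive. A site that stops at its serum bullet may not treat a transient rise as an event. Section 4 plans for about 80 children in Treatment Period 1, so consistent handling of even a few such cases is worth having.

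**Working it through.** The protocol gives no figure to reproduce and no formula applies. The check is a comparison of the texts.

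| Element | Section 7.4 | Table 15-1, lower tier | Table 15-1, upper tier |
|---|---|---|---|
| Label | Serum event | Serum event | Serum event (acute kidney injury) |
| Rise over baseline | at least 25% | 25-49% | at least 50% |
| Above normal | yes, for gender and age | yes, above ULN | yes, above ULN |
| Confirmation | after at least 24 h | after 24-48 h | none stated |
| Persistence | at least 3 consecutive months | none | none |
| Timed follow-up | none of its own; refers to Appendix 3 | within 2-5 days | within 24-48 h if possible |

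**Where they agree.** Together the two tiers of the table cover rises from 25% upward, which is the Section 7.4 threshold. The above-normal condition matches in substance. Confirmation after about a day appears in Section 7.4 and in the lower tier. The substantive conflict is the persistence row.

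**Test cases, each assumed confirmed and above normal limits.**

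1. A 30% rise that resolves in 2 weeks: lower-tier serum event in Table 15-1; not a serum event in Section 7.4.
2. A 60% rise that settles in 8 weeks: acute kidney injury in Table 15-1; not a serum event in Section 7.4, because 8 weeks is short of 3 months.
3. A 30% rise lasting longer than 3 months: a serum event in both. Under Section 7.4 this is established only once the 3 months have passed, after the 24-48 hour and 2-5 day windows have closed.

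The classifications therefore differ for every qualifying rise that resolves within 3 months.

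**Is the 3-month condition explained elsewhere?** Appendix 1 uses the phrase "decrease from baseline, ≥ 3 months in duration" for creatinine clearance, and a 3-month duration for new dipstick protein. Its serum creatinine criterion, at least 1.5 times ULN, has no duration. Apart from Section 7.4, the protocol places no 3-month condition on serum creatinine.

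**The case against.** The strongest defence is that sites act on Table 15-1 and not on the bullet. The only action sentence in Section 7.4 ties follow-up to the table's definition, and the CRF instruction also sits in the table. This stands. A reader might infer that the 3-month wording defeats the timed follow-up altogether, but the document does not support that: a site that follows the reference would still act within days. The 3 months is the time needed to meet a persistence condition, not the time needed to notice a raised creatinine.

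A reader might also infer that renal safety becomes uninterpretable or that event counts in the report would be unreliable. The document does not support that either. Section 9.4.4 lists no renal-event endpoint. Section 9.4.4.3 summarises laboratory data by descriptive statistics, shift tables and the Appendix 1 notable criteria. Creatinine is measured centrally (Sections 6.5.5 and 8.3), so those summaries do not depend on how a site labels an event. Whether a laboratory value is an adverse event is governed by the separate criteria in Section 7.1.

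Finally, a two-level scheme is conceivable, with Table 15-1 as an early alert and Section 7.4 as a sustained event. Section 7.4 does mention both a trigger and an event. But it never separates them, both places use the same label, and Section 7.4 points to the table for the definition. Where the protocol intends two levels, as for the liver in Section 7.3, it names each and describes its follow-up. The two-level reading is a possible intention, not something the text states.

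**Conclusion.** The inconsistency is real and limited to one condition. Section 7.4 requires at least 3 consecutive months and Table 15-1 requires no duration, under one label and with a cross-reference that makes the table the source. The consequence is a risk that a site relying on the Section 7.4 bullet does not flag, document or follow up a rise that resolves within 3 months. How often this would happen cannot be estimated from the protocol, which gives no expected rate of creatinine rises. The conclusion assumes that the two serum event headings are meant to describe the same thing, which is what the cross-reference says. The primary analysis and the planned Appendix 1 laboratory summaries are not affected.

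**What to change.** Reconcile Section 7.4 with Table 15-1 so that one definition of the serum event governs alerts, follow-up and CRF documentation. If the 3-month condition is meant for a separate sustained renal outcome, give it its own name, state what it is used for, and take it out of the definition that leads to Appendix 3. Which criterion applies clinically is for the sponsor to decide. The cost is a wording change in Section 7.4 or Appendix 3, with no new test or visit.

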7.5 Reporting of study treatment errors including misuse/abuse

Medication errors are unintentional errors in the prescribing, dispensing, administration or monitoring of a medicine while under the control of a healthcare professional, patient or consumer (EMA definition).

Misuse refers to situations where the medicinal product is intentionally and inappropriately used not in accordance with the protocol.

Abuse corresponds to the persistent or sporadic, intentional excessive use of a medicinal product, which is accompanied by harmful physical or psychological effects.

Study treatment errors and uses outside of what is foreseen in the protocol will be collected in the DAR (dose administration record) eCRF page irrespective of whether or not associated with an AE/SAE and reported to Safety only if associated with an SAE. Misuse or abuse will be collected and reported in the safety database irrespective of it being associated with an AE/SAE.

Table 7-1 Treatment Errors

Treatment error type	Document in Dose Administration (DAR) eCRF (Yes/No)	Document in AE eCRF	Complete SAE form
Unintentional study treatment error	Yes	Only if associated with an AE	Only if associated with an SAE
Misuse/Abuse	Yes	Yes,	Yes, even if not associated with a SAE

7.6 Pregnancy reporting

To ensure patient safety, each pregnancy occurring after signing the informed consent must be reported to Novartis within 24 hours of learning of its occurrence. Where possible, the pregnancy should be followed up to determine outcome, including spontaneous or voluntary termination, details of the birth, and the presence or absence of any birth defects, congenital abnormalities, or maternal and/or newborn complications.

Where possible, pregnancy must be recorded on the Pharmacovigilance Pregnancy Form and reported by the Investigator to the local Novartis Drug Safety and Epidemiology Department. Pregnancy follow-up should be recorded on the same form and should include an assessment of the possible relationship to the study treatment.

Any SAE experienced during the pregnancy and unrelated to the pregnancy must be reported on a SAE form.

8 Data review and database management

8.1 Site monitoring

Before study initiation, at a site initiation visit or at an investigator's meeting, a Novartis representative will review the protocol and data capture requirements (i.e. eCRFs) with the investigators and their staff. During the study, Novartis employs several methods of ensuring protocol and Good Clinical Practice (GCP) compliance and the quality/integrity of the sites' data. The field monitor will visit the site to check the completeness of patient records, the accuracy of data capture / data entry, the adherence to the protocol and to Good Clinical Practice, the progress of enrollment, and to ensure that study treatment is being stored, dispensed, and accounted for according to specifications. Key study personnel must be available to assist the field monitor during these visits. Continuous remote monitoring of each site's data may be performed by a centralized Novartis CRA organization. Additionally, a central analytics organization may analyze data & identify risks & trends for site operational parameters, and provide reports to Novartis Clinical Teams to assist with trial oversight.

The Investigator must maintain source documents for each patient in the study, consisting of case and visit notes (hospital or clinic medical records) containing demographic and medical information, laboratory data, electrocardiograms, and the results of any other tests or assessments. All information on CRFs must be traceable to these source documents in the patient's file. The Investigator must also keep the original informed consent form signed by the patient/guardian (a signed copy is given to the patient/guardian).

The Investigator must give the monitor access to all relevant source documents to confirm their consistency with the data capture and/or data entry. Novartis monitoring standards require full verification for the presence of informed consent, adherence to the inclusion/exclusion criteria, documentation of SAEs, and of data that will be used for all primary variables. Additional checks of the consistency of the source data with the CRFs are performed according to the study-specific monitoring plan. No information in source documents about the identity of the patients will be disclosed.

